Properly secure the sensor of choice (as depicted in Appendix 8). Press measurement start-up. The monitor will start the measurement by setting the stimulus current automatically and by performing a reference measurement. This will be done during induction, before administration of any muscle relaxant. Depolarizing relaxants result in an equal drop in all four responses, without fade. Non-depolarizing relaxants cause a fade in the responses, indicated by a lower TOF% and a slope in the bar graph. Neuromuscular block Is used to facilitate endotracheal intubation. The anesthesia provider can use the time when all responses disappear (i.e., TOF Count is 0) as a guide to determine when to intubate. During surgery, TOF Count is used to maintain a steady optimal level of neuromuscular block. When TOF Count exceeds a level set by the user, the GE monitor will give a "Block recovery" message.

TOF monitoring will occur every minute during the procedure. This will allow for recovery at the neuromuscular junction after post-tetanic stimulation. Administration of additional muscle relaxant will not be allowed. Patients will be maintained in their respective randomized groups (moderate versus deep) and treated unless a change or deterioration in the clinical condition requiring additional muscle relaxant occurs, at which point, such patient will be dropped from the study.

Muscle relaxation will be maintained until abdominal fascia closure, defined as when abdominal incision openings of all port sites are surgically closed. All patients will be reversed using sugammadex as per manufacturer's dosing recommendations: for TOF greater than 2, administer 2 mg/kg; for PTC greater than or equal to 1, administer 4 mg/kg; for PTC of less than 1, investigators will wait until PTC count recovers to 1 and then give 4 mg/kg.. More detailed recommendations are outlined in Appendix 5.

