Current standard of care for patients undergoing robotic prostactectomy is moderate blockade (i.e. 1-2 twitches on TOF). Patients in either arm of the study will receive AT LEAST as much blockade as current standard of care. It is extraordinarily unlikely that surgical investigators in this study will demand deeper neuromuscular blockade than a moderate blockade. If a surgeon requests deeper blockade, they will be reminded that the patient is in protocol and that depth of blockade will be at least moderate blockade as per current standard of care. The surgeon will remain blinded to the depth of neuromuscular blockade. In the case a surgeon assesses that deeper blockade is necessary for a given patient, the anesthesia provider will give additional neuromuscular blockade.

Estimated blood loss and total surgical operative time will be extracted from Electronic Medical Record. Postoperatively, endpoints (pain and nausea) will be recorded on all patients by a PACU nurse according to pain and nausea scales. The 24 and 48-hour assessments will be captured via telephone by the research staff. 

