#### 13.0 CRITERIA FOR REMOVAL FROM STUDY

Criteria for removal of subject from the study will include patient death, surgical conversion from robotic to open procedure, intraoperative deterioration in clinical condition that would end a planned procedure.

Patients are considered evaluable for the first primary endpoint (IAP) if they can provide at least one IAP recording; patients are considered evaluable for the second primary endpoint (Pain) if they can provide at least one NPS pain score within 6-hours after surgery. Study data will be analyzed according to a modified intention-to-treat principle ("modified" because patients considered inevaluable for a given primary endpoint will be excluded from the analysis of that endpoint).

The following are a list of possible perioperative scenarios. We expect these to occur extremely infrequently. We anticipate fewer than 10 occurrences during the study period and have planned the protocol accordingly.

- 1) Cancelled surgery
  - Patient will not provide either primary endpoint therefore patients in this category will be excluded from primary analysis
- 2) Patient death
  - For patients who die in the perioperative period, any data up until patient death will be analyzed. These patients may possibly contribute data for only one of the two primary endpoints (IAP)
- Surgical conversion from robotic to open procedure
   Any data up until conversion will be analyzed.

   These patients may possibly contribute data for only one of the two primary endpoints (IAP)
- 4) Intraoperative deterioration in clinical condition that would end planned procedure For patients who experience deterioration in clinical condition that ends planned procedure, any data up until deterioration will be analyzed.
  - However, there will be an investigation to assess the possible (but extraordinarily unlikely) influence of protocol in leading to deterioration.
- 5) Deviation from protocol by giving additional dose of NMB to satisfy surgeon request for better visualization
  - All data in this scenario will be analyzed.. Secondary analysis will be conducted as treated.
- 6) Equipment failure of the neuromuscular train of four monitoring device
  Any data up until failure of neuromuscular train of four monitoring device will be analyzed.patient will
  be considered evaluable for only one of the two primary endpoints (IAP).
- Accidental unblinding of surgeon
   All data will be analyzed.. This will be an evaluable patient.

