For the second primary endpoint based on postoperative pain, we will collect all NPS pain scores within the 6-hours postoperation and will express results as AUCpain at the patient level. In a retrospective analysis of 37 patients from a similar population (See Section 3.8), mean pain level within the 6-hours postoperation was 1.3 (SD of 0.5) on the **log-transformed NPS scale**.

Sample size calculation is based on the mean AUCIAP and AUCpain within 6-hours postoperation across patients in each arm. We power this study with 2 primary endpoints to detect 20% decrease in IAP (from 13.9 to 11.1, SD of 4) and 25% decrease in pain scores within the 6-hours postoperation (from 1.3 to 0.975; SD of 0.5) with deep vs moderate NMB, with type I error rate of 0.025 for each endpoint. The change in NPS scores (25% or 1 point on the raw scale) is a validated clinically meaningful change. The decrease in pain scores on which the sample size estimate is based on the natural log transformed scores. This calculation assumes independence of the two primary endpoints. We elected to increase the standard deviation of the AUCIAP in this power calculation as a conservative measure because the population from the reference study is different from the population of interest. A total of 120 patients evaluable for each of the primary endpoints will provide 90% power to detect a significant difference in at least one of the two endpoints. This sample size also allows for an interim analysis halfway through enrollment, using O'brien-Fleming boundaries with Lan de Mets spending functions for futility. We base the interim analysis decision rule on both of the primary outcomes. The trial will continue to full enrollment if the interim analysis results for either/both of the primary outcomes reports p<0.755. The trial may be terminated if p>0.755 for both outcomes. We will conclude that the arms are significantly different if p≤0.025 for either of the outcomes. In order to ensure at least 120 patients evaluable for each of the primary endpoints, we plan to randomize at least 130 patients (See Section 13.0 for potential perioperative scenarios).

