Analysis of the primary endpoint which involves IAP will be AUCIAP compared between the two arms using the linear mixed-effects model: randomized arm as the fixed-effect, BMI as the adjustment covariate, with surgeon-level random effects. Transformation of the outcome may be applied if the normality-of-errors assumption is violated. As a secondary analysis, the longitudinal IAP measurements will be analyzed using linear mixed-effects models including time and randomized arm as fixed-effects with stratification variable (BMI), and patient-level random effects, nested within surgeons. In the rare case that the patient's IAP is beyond 15 the surgeon will be unblinded to the IAP, and only the IAP up to the point of unblinding will be included in the analysis. 15 is the conventional goal for the upper limit of IAP at MSKCC. Investigators request they know the IAP at a level of 15, so they can weigh risk/benefit of continuing to operate at that higher threshold of IAP. In this rare occurrence, patients will still be included in the analyses as modified intent-to-treat, including IAP values until IAP-unblinding.

Analysis of the second primary endpoint will be AUCpain within 6-hours postoperation. AUCPain analysis will be conducted with linear mixed-effect model with appropriate transformation for the outcome for normality. The model will include randomized arm as fixed-effects along with stratification variable (BMI), and patient-level random effects, nested within surgeons.

For the primary analyses, all recorded IAP will be analyzed in a modified intent-to-treat fashion. Where a patient randomized to moderate NMB crosses over to deep NMB, all recorded IAP will be analyzed under the randomized arm. As a secondary analysis of the primary outcome, we will perform an as-treated analysis where the set of IAP values will be assigned to the actual intervention received. Correlation between AUCIAP and AUCPain will be summarized using Spearman correlation coefficient. Additionally, the primary endpoints will be summarized between patients with and without neuromonitoring issues (see

Section 13.0). As a sensitivity analysis, planned analyses of both primary endpoints will be repeated after excluding patients with neuromonitoring issues (see Section 13.0).

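### The secondary as-treated analysis of IAP regroups control patients because their exposure was poor, so it is biased against deep block; a pre-defined complier estimate is the better secondary analysis

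*Combined protocol and SAP*

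**What the plan says.** The primary IAP analysis in Section 14.0 is modified intention to treat: "Where a patient randomized to moderate NMB crosses over to deep NMB, all recorded IAP will be analyzed under the randomized arm". A further, secondary analysis follows: "we will perform an as-treated analysis where the set of IAP values will be assigned to the actual intervention received".

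The route to crossover is given elsewhere. Section 4.2: "In the case a surgeon assesses that deeper blockade is necessary for a given patient, the anesthesia provider will give additional neuromuscular blockade". Section 13.0, scenario 5, lists "Deviation from protocol by giving additional dose of NMB to satisfy surgeon request for better visualization", keeps all data from such patients, and adds: "Secondary analysis will be conducted as treated". An earlier paragraph of Section 4.2 rules out additional relaxant. It says of a patient who needs it after a clinical change that "such patient will be dropped from the study".

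On frequency, Section 13.0 says of its listed scenarios together: "We anticipate fewer than 10 occurrences during the study period". The documents give no figure for crossovers alone. They set no threshold at which a control patient counts as having received deep block. They do not say whether that patient's IAP values move whole or are split at the extra dose.

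**The concern.** Poor exposure does two things in this trial. It leads the surgeon to ask for more pressure (Section 4.1, IAP pressure maintenance), and it triggers the additional relaxant. Regrouping patients by relaxant received therefore selects on a cause of the outcome. Patients who tend to high IAP leave the control group and enter the deep group, so control looks better and deep looks worse.

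This is the only planned analysis of the effect of treatment received; the per-protocol analysis in Section 14.0 concerns accidental unblinding. At stake is how a secondary result reads beside the primary one. It could understate a real benefit, or suggest harm where there is no effect. No caveat or alternative is planned.

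**Working it through.** **Inputs from the documents.** Section 14.0 plans to "detect 20% decrease in IAP (from 13.9 to 11.1, SD of 4" mmHg. The difference is D = 13.9 - 11.1 = 2.8, and 2.8/13.9 = 20.1%, which agrees with the stated 20%. The SD is s = 4; the reference study's SD, also in Section 14.0, is 1.3. There are 130/2 = 65 patients per arm. Fewer than 10 deviations are expected, so k = 9 control crossovers is an upper bound and k = 3 an illustration.

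**Assumptions.** Crossovers are the control patients with the highest scores on a need variable that has correlation r with their own IAP. Each spends a share f of the case at deep block, and the effect is proportional to that share. Deep-arm patients are at deep block throughout. The documents give neither r nor f; the base case is r = 0.5, f = 1.

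**Formulas.** Differences are written as reductions under deep block. Let c = k/65, let z be the upper-c normal quantile and p the normal density at z.

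- Crossovers exceed the control mean by r·s·p/c; the other controls fall below it by r·s·p/(1 - c).
- Intention to treat (ITT) = D(1 - c·f).
- As-treated, whole patients, f = 1: D - 2·r·s·p/(1 - c²).
- Complier estimate, binary definition: ITT/(1 - c). By share of time: ITT/(1 - c·f).

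**Numbers, r = 0.5, s = 4, f = 1.**

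- k = 3: c = 0.0462, p = 0.0967. ITT = 2.8 × 0.9538 = 2.67. As-treated = 2.8 - 2(0.5)(4)(0.0967)/0.9979 = 2.8 - 0.39 = 2.41. Complier = 2.67/0.9538 = 2.80.
- k = 9: c = 0.1385, p = 0.2209. ITT = 2.8 × 0.8615 = 2.41. As-treated = 2.8 - 2(0.5)(4)(0.2209)/0.9808 = 2.8 - 0.90 = 1.90. Complier = 2.41/0.8615 = 2.80.

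The subtracted term does not contain D. With D = 0 the as-treated analysis therefore shows 0.39 (k = 3) or 0.90 mmHg (k = 9) higher IAP under deep block.

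**Sensitivity (k = 3; k = 9).**

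| Setting | ITT | As-treated, whole | Complier, binary |
|---|---|---|---|
| s = 4, r = 0.25, f = 1 | 2.67; 2.41 | 2.61; 2.35 | 2.80; 2.80 |
| s = 4, r = 0.5, f = 1 | 2.67; 2.41 | 2.41; 1.90 | 2.80; 2.80 |
| s = 4, r = 1, f = 1 | 2.67; 2.41 | 2.02; 1.00 | 2.80; 2.80 |
| s = 1.3, r = 0.5, f = 1 | 2.67; 2.41 | 2.67; 2.51 | 2.80; 2.80 |
| s = 4, r = 0.5, f = 0.5 | 2.74; 2.61 | 2.35; 1.73 | 2.87; 3.02 |

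In the last row, splitting values at the extra dose instead of moving them whole gives 2.61; 2.36. The complier estimate by share of time gives 2.80 in both cases, for example 2.61/(1 - 0.0692) with k = 9.

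**Simulation check** (4,000 trials per setting, 60 per arm, s = 4, r = 0.5, f = 1, two-sided 0.025). Power is 93% for ITT and 86% for as-treated with 3 crossovers, and 86% and 64% with 9. With no true effect, the as-treated type I error is 4.8% with 3 crossovers and 17% with 9.

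**Precision.** The SE of the complier estimate is that of ITT divided by (1 - c): 1/0.9538 = 1.05 with 3 crossovers and 1/0.8615 = 1.16 with 9.

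**The case against.** The strongest reply is limited reach. Crossovers stay in their randomised arm in the primary analysis, success is judged on the primary endpoints at 0.025, and no decision rule uses the as-treated result. The plan expects few deviations of any kind, and Section 4.2 regards a surgeon's demand for more than moderate block as very unlikely. All of this stands and limits the point to a secondary analysis.

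Four stronger readings might be inferred, and the documents do not support them.

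- That the bias always runs towards no effect. It runs against deep block; that is towards the null only if deep block truly helps.
- That crossover could reach a fifth of controls. That would be 13 of 65, more than the plan allows for all scenarios in both arms.
- That as-treated is always worse than ITT. At SD 1.3 with r = 0.5 and full-case exposure it is equal or closer to 2.8.
- That an instrumental-variable estimate answers the same question free of bias. It estimates the effect in patients who would follow their assignment, whereas as-treated compares groups by treatment received. It needs the exclusion restriction, its test adds little beyond ITT, and a binary definition overshoots when extra block covers only part of the case.

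A split at the extra dose would also shrink the bias, though it brings in time-related confounding of uncertain sign. The plan does not say that values are split.

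**Conclusion.** The concern holds for the secondary as-treated analysis only. If values move whole, selection on poor exposure biases it against deep block. At SD 4 and an assumed correlation of 0.5, with full-case exposure, a true 2.8 mmHg becomes about 2.4 with 3 crossovers and 1.9 with 9, and a null effect becomes a false 0.4 to 0.9 mmHg against deep block. The size rests on the number of crossovers, the strength of selection and the share of the case affected, none of which the documents give; at SD 1.3 it is small. A reader might infer that the trial's main IAP conclusion is at risk. It is not, because the modified intention-to-treat analysis does not use this regrouping. The point is a cheap improvement to a secondary analysis.

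**What to change.** 1. Make the complier average causal effect the planned secondary estimate of the effect of treatment received: two-stage least squares with randomised arm as instrument, adjusted for BMI and surgeon. Do not move any patient's IAP between arms.
2. Define deep block received before the data are examined, from the recorded train-of-four and post-tetanic counts and the protocol's own definition of deep block. Preferably use the proportion of insufflation time at deep block, because a binary definition gives about 2.9 to 3.0 instead of 2.8 when extra block covers half the case. State whether original or corrected train-of-four values are used.
3. State that this is a different estimand, that it needs the exclusion restriction, and that its test adds little to ITT.
4. If the as-treated analysis is kept, label it exploratory, say whether values move whole or are split, and state the expected bias against deep block.
5. Reconcile the two statements in Section 4.2 and scenario 5 of Section 13.0 on patients given additional relaxant, so that it is clear whose data are kept and who could count as a crossover.

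The cost is SAP wording, timed depth-of-block data for each patient, and an SE about 5% larger with 3 crossovers and about 16% larger with 9.

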#### Secondary Hypotheses:

- 1) Deep NMB will result in improved surgical exposure (assessed by the surgeon) during robotic surgery
- 2) There will be an improvement in outcomes of various exploratory endpoints as a result of deep NMB. These endpoints include: the total dose of analgesics during the procedure, the total dose of analgesics postoperatively, postoperative shoulder pain, total intraoperative blood loss, operating time, postoperative nausea, time to first *postoperative* antiemetic, total dose of antiemetics postoperatively, and postoperative RASS scores (Richmond Agitation Sedation Scale)

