#### Postoperative nausea:

As per the standard of care at the Josie Robertson Surgery Center, the PACU nurses that have been trained by the PI and blinded to randomization will ask the patient to rate their nausea. The actual question asked is "on a scale of 0-10, where 0 is no nausea and 10 is the worst nausea imaginable, please rate your nausea." The nausea assessment will be administered verbally.

The PACU nurse will record postoperative nausea and vomiting (PONV) in PACU (one-hour post-extubation) and at postoperative times of 1-hour, 6-hour, and 12-hour on the research assessment form., The 24 and 48-hour time points will be completed via telephone by the research staff on the research assessment form if the patient has been discharged before these time points are assessed.

The Apfel 4 point scale for predicting postoperative nausea and vomiting will be used. This scale includes four predictors: female gender, history of motion sickness, nonsmoking, and use postoperative opioids. As all patients in the protocol for robotic prostatectomy will be male, Apfel score will not exceed 3 in any patient. If patient received EMEND preoperatively, the patient will be included in study but the nausea data will be excluded. PONV will be assessed with a scale of 0-10 (0=no nausea and 10 worst nausea imaginable)

In addition, the total dose of rescue antiemetics in the postoperative period will be recorded.

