Although the occurrence will probably be rare, accidental unblinding will be recorded as a protocol violation as part of standard reporting procedure. According to the ICH E9 Statistical Principles for Clinical Trials, usually of violations that occur post-randomization, it is appropriate to include the data from such subjects in the analysis, consistent with the modified intention-to-treat principle. We will include these cases in the primary analysis of the primary outcome in the randomized arm. For each case of major protocol violation, we will enroll an additional patient randomized and included in the analyses. Also, we will perform per protocol analysis that excludes patients who had accidental unblinding.

Surgeon assessment of surgical conditions (continuous measure, on a 1 to 5 scale) recorded every 30 minutes, will be analyzed with linear mixed-effects models as above.

Estimated blood loss (EBL) will be compared between the two arms using linear mixed-effects model (randomized arm and BMI fixed-effects variables, and surgeon-level random effect), accounting for duration of surgery if necessary (i.e., rate of EBL). Transformation of the outcome may be applied if the normality-of-errors assumption is violated.

Postoperative pain (surgical and shoulder pain, 0 no pain to 10 worst pain imaginable), defined at postoperative 1-hour, 6-hour, 12-hour, 24-hour, and 48-hour post operation will be compared between the two arms using linear mixed-effects models with appropriate transformation for the outcomes for normality.

The model will include patient-level random effects (nested within surgeons), treatment arm, and time as fixedeffects, along with stratification variable (BMI) as adjustment factors. To address potential confounding due to history of chronic pain, patients with chronic pain will be excluded from protocol. Chronic pain will be defined as a patient on a sustained-release opioid in the last 3 months. Besides patient-reported pain scores, perioperative analgesia use will be analyzed similarly to the pain scores: intraoperative cumulative IV analgesia use will be compared between the two arms after adjusting for duration of surgery; while postoperative IV analgesia use will be analyzed as cumulative total dose within the first 6-hours post surgery and until prior to discharge (with adjustment for duration of postoperative stay in the analysis).

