Postoperative nausea (measured at the same intervals) will also be analyzed with linear mixed-effects models. To address potential confounding due to preoperative risk for nausea, the model will include adjustment for preoperative Apfel score (4 point scale with a maximum of 3 points due to an all male patient population) and preoperative EMEND use. In addition to patient-reported nausea scores, postoperative antiemetic use will be analyzed in the following fashion: the use of any antiemetics will be analyzed with a mixed-effects logistic regression model, and the use of any antiemetics within the first 6-hours post surgery and until prior to discharge will be analyzed with linear mixed-effects models. Time to first rescue antiemetic medication will also be recorded and compared between the two arms using Kaplan-Meier approach and log-rank test.

We will assess the relationship between the treatment arms and operating time (defined as the time between incision to surgery end) using a linear mixed-effects model with transformation for the outcome for normality. The model will include treatment arm and stratification variable (BMI) and surgeon-level random effect

Richmond Agitation Sedation Scale (RASS) scores, measured at 1, 6, 12, 24 hours postperatively will be modeled and compared between the two arms using linear mixed-effects model. The model will include treatment arm and stratification variable (BMI) and surgeon-level random effect.

One primary concern from deep paralysis is postoperative pulmonary complications and the need for reintubation and prolonged postoperative intubation. All patients who receive neuromuscular blockade are at 23

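### Total analgesic use is adjusted for duration of surgery and length of stay, both of which arise after randomisation and may respond to the arm

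*Combined protocol and SAP*

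**What the plan says.** All references are to the combined protocol and SAP.

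- **Endpoints.** Section 2.0 (Secondary Objectives and Secondary Hypotheses) names total analgesic dose during the procedure, total analgesic dose afterwards, total intraoperative blood loss and operating time. The hypothesis is: "There will be an improvement in outcomes of various exploratory endpoints as a result of deep NMB".
- **Intraoperative analgesia (14.0).** "intraoperative cumulative IV analgesia use will be compared between the two arms after adjusting for duration of surgery". No condition is attached.
- **Postoperative analgesia (14.0).** "postoperative IV analgesia use will be analyzed as cumulative total dose within the first 6-hours post surgery and until prior to discharge", followed in parentheses by "with adjustment for duration of postoperative stay in the analysis". From its position, the stay adjustment belongs to the until-discharge total and not to the 6-hour total, but the text does not say so outright.
- **Blood loss (14.0).** The base model has arm and BMI as fixed effects and a surgeon random effect. Duration enters only conditionally: "accounting for duration of surgery if necessary (i.e., rate of EBL"). No criterion for necessity is given.
- **Operating time (14.0).** It is compared by arm as an outcome, with BMI and surgeon in the model.
- **Timing (15.2).** Randomisation follows registration, so it precedes surgery.
- **Primary IAP model (14.0).** It contains arm, BMI and surgeon. Neither primary model contains duration or stay.

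**The concern.** A covariate measured before randomisation can only sharpen an arm comparison. One measured afterwards may itself be a result of the arm. Adjusting for it then does two things. It removes whatever part of the arm's effect runs through the covariate: a shorter operation that needs less opioid would get no credit for being shorter. It also makes the arms unlike in anything else that drives the covariate. Among operations of equal length, if deep blockade speeds surgery, the deep-arm cases are on average the harder ones, and harder cases may need more analgesia whatever the arm.

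At stake is the reading of the analgesic endpoints. Section 2.0 asks about total dose. The planned model answers a different question, and nothing in section 14.0 labels it as different.

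**Working it through.** **Can the arm move the covariates, on the plan's own account?**

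- *Duration of surgery.* Yes. Section 2.0 lists operating time among the endpoints expected to improve, and section 14.0 tests it by arm. Section 3.6 gives an opposing route: higher IAP is associated with shorter operations, so the lower IAP expected under deep blockade could lengthen them. The net direction is open, but both routes make duration a possible consequence of treatment.
- *Length of stay.* The documents state no hypothesis. Section 16.0 merely lists it among data to be collected. An arm effect is possible but is not claimed.

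**Size.** The plan gives no SD, slope or expected difference for analgesic dose or duration, so there is no plan figure to reproduce. Every input below is an assumption, in SD units, apart from 60 per arm (120 evaluable patients, 1:1).

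Let the arm A shift duration M by *a*, let an unmeasured difficulty U act on M with weight *d* and on the outcome Y with weight *c*, and let M act on Y with slope *b*. There is no other arm effect:

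- M = aA + dU + noise; Y = bM + cU + noise
- Total effect of the arm = a × b
- Given A and M, the mean of U is d(M − aA), so the adjusted arm coefficient = −a × c × d

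The simulation used 120 patients, 5,000 runs per row and a two-sided 0.05 test:

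| a | b | c × d | Total effect a × b | Adjusted, by formula | Simulated unadjusted | Simulated adjusted | Rejection, unadjusted / adjusted |
|---|---|---|---|---|---|---|---|
| 0 | 0.5 | 0.4 × 0.4 = 0.16 | 0 | 0 | 0.00 | 0.00 | 4.5% / 5.1% |
| −0.3 | 0.5 | 0 | −0.15 | 0 | −0.15 | 0.00 | 12.6% / 5.5% |
| −0.3 | 0.5 | 0.16 | −0.15 | +0.05 | −0.15 | +0.05 | 11.6% / 6.2% |
| −0.5 | 0.5 | 0.16 | −0.25 | +0.08 | −0.26 | +0.08 | 28.5% / 8.5% |
| −0.3 | 0 | 0.5 × 0.5 = 0.25 | 0 | +0.08 | 0.00 | +0.08 | 4.7% / 6.8% |
| −0.5 | 0 | 0.25 | 0 | +0.13 | 0.00 | +0.13 | 5.0% / 10.5% |

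Row 1: if the arm leaves duration alone, adjustment is harmless. Row 2: with no shared cause, adjustment removes the real effect through duration. Rows 3 and 4: with a shared cause, the sign reverses. Rows 5 and 6: with no effect on the outcome at all, a spurious one appears.

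**Sensitivity to the assumed slope.** Take a shift of 0.25 SD and an outcome slope *s* on duration that comes wholly from difficulty. Bias = 0.25 × s and SE = √(2/60) × √(1 − s²).

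- s = 0.3: bias 0.08, SE 0.174, false-positive rate 7%
- s = 0.5: bias 0.13, SE 0.158, false-positive rate 12%
- s = 0.6: bias 0.15, SE 0.146, false-positive rate 18%

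The spread from 7% to 18% comes entirely from the choice of *s*.

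**The case against.** The best defence is that dose accumulates with time, so a duration-adjusted dose is less noisy and answers a fair question about intensity of use. The two routes to operating time may cancel. Operating time is reported by arm, so a reader can see whether the condition for bias is met. Surgeon and BMI in the model may absorb some case difficulty. The 6-hour window is already planned. All these endpoints are exploratory.

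Much of this stands. It makes the problem conditional and keeps its priority low. Two parts do not settle it. The intensity question is legitimate, but it is not the endpoint named in section 2.0. And the operating-time comparison is a weak safeguard: with 60 per arm its 95% interval has a half-width of about 1.96 × √(2/60) = 0.36 SD, so shifts as large as those in several rows above could pass unnoticed.

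A reader might also infer more than the documents support:

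- **Nausea adjusted for an outcome.** The Apfel items in section 4.1 end with "nonsmoking, and use postoperative opioids", which could suggest that observed opioid use enters the nausea model. But section 14.0 specifies "adjustment for preoperative Apfel score", and nowhere do the documents say that actual use is scored. At most the source of that item needs clarifying.
- **Blood loss adjusted for duration.** The base model already omits duration. The gap is the missing criterion for switching to a rate.
- **Stay adjustment certainly biased.** That would need an arm effect on stay, which the documents do not assert.
- **False-positive rates of 12% or 18% as a forecast.** They require the whole slope to come from difficulty, with operating time itself causing no analgesic use. That is hard to credit for a cumulative intraoperative dose.

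**Conclusion.** The point holds in conditional form. As written, the intraoperative analgesic comparison, and the until-discharge comparison as most naturally read, condition on variables that follow randomisation. If the arm changes those variables, the estimates are not the arm's effect on total dose and can be distorted in either direction by shared causes. If it does not, nothing is lost. The condition is live for duration, because the protocol hypothesises a change in operating time. For stay it is only a possibility.

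The size cannot be taken from the documents. The figures above show mechanism and direction under assumed inputs, and they predict nothing about this trial. Neither primary analysis contains these covariates, so the trial's main conclusion, sample size and power are unaffected. This is a cheap improvement of low severity.

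**What to change.** Changes to section 14.0:

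1. **Intraoperative analgesia.** Make the model with arm, BMI and surgeon, without duration, the main analysis of total dose. Report the duration-adjusted result as supportive, and say that it does not estimate the total effect of the arm.
2. **Postoperative analgesia.** Make the planned first-6-hour total the main measure and state that it carries no stay adjustment. Keep the stay-adjusted until-discharge result as a labelled supportive analysis.
3. **Blood loss.** Keep the existing arm, BMI and surgeon model as the main analysis. Report the rate only as supportive, in place of the open-ended choice.
4. **Nausea (clarification only).** State that the opioid item of the Apfel score is scored from information available before randomisation.

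The cost is SAP wording, with no new data and no change to the 120 evaluable patients. The drawback is that total doses are somewhat noisier than duration-adjusted ones. The adjusted results remain available alongside.
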